
8.2 Analysis *Without Imputation*

Using the same normal scores for percentiles of rank methodology described above (section 7.1), we will compare the treatment groups *without imputation of any missing 24-month CT measurements of the MTD of the aneurysm*.

8.3 Analysis of Per-Protocol Population

An analysis will be performed using the methodology described above for the primary endpoint, based on the per-protocol population.

8.4 Changes from Protocol-Specified Efficacy Analyses

The primary efficacy analysis population has been renamed the “full analysis population” rather than the “intention-to-treat population” to avoid dispute over whether exclusion of patients for whom there are no follow-up visits or follow-up CT scans represents an imperfection in an “intention-to-treat” analysis plan or a different study population.

9 Interpretation of the Primary Outcome

Interpretation of the primary outcome analysis must be cognizant of N-TA³CT as a Phase IIb clinical trial. The primary outcome is based primarily on anatomical measurements instead of clinical events. Benefit in the primary outcome could influence physician behavior for off label use, but is not going to result in a labeled indication. In particular it cannot be expected that we will know whether or not doxycycline effects on abdominal aortic aneurysm diameter are associated with the occurrence of rupture or the diameter at which risk of rupture outweighs the risk associated with repair. Effects on rupture or mortality could be observed fortuitously, and would have to be interpreted as secondary outcomes. If the investigators reject the null hypothesis, they have a considerable responsibility to assure that they have not introduced bias and explain to the medical community their basis for believing that bias is not the reason for rejecting the null hypothesis. If the investigators fail to reject the null hypothesis, they have a considerable responsibility to assure that they have performed a sensitive test, i.e., not introduced bias through defects in study design (especially power calculation assumptions) and performance (especially adherence or missing data), and explain to the medical community their basis for believing that bias is not the reason for failing to reject the null hypothesis.

Interactions:

With gender: If there is a statistically significant interaction ($p \leq 0.05$) between the effect of doxycycline in men and the effect in women, there will be a search for explanations for the interaction. For example, adherence will be examined. The gender strata will be analyzed separately in the event of an important interaction. If there are important, non-significant differences between the gender strata, e.g., no effect in one stratum and a 40% effect size in the

Non-Invasive Treatment of Abdominal Aortic Aneurysm Clinical Trial

N-TA³CT

STATISTICAL ANALYSIS PLAN

other, there will be a search for explanations for the differences between the strata, and the separate strata will be analyzed according to the standards of secondary analyses.

With Clinical Site: Influence of clinical site on treatment effects will be inspected. If there are outlier clinical sites, explanations for the inhomogeneity will be sought (e.g., differences in adherence) and any differences or inhomogeneities found will be presented with the primary analysis.

The findings of the primary outcome analysis in the full analysis population may reject or fail to reject the null hypothesis. Rejection of the null hypothesis with a median growth $\geq 40\%$ less in the doxycycline group than in the placebo group would be evidence of both a statistically significant and clinically significant effect.

Results of analysis of the Full Analysis Population Conflict with Results from the Per-Protocol Population

If the primary outcome analyses based on the full analysis population and per protocol population are in agreement rejecting the null hypothesis or failing to reject the null hypothesis, we will reject or fail to reject the null hypothesis accordingly. If the analysis based on the full analysis population fails to reject the null hypothesis but the analysis based on the per protocol population rejects the null hypothesis, we will interpret the findings to indicate that doxycycline may be but has not been demonstrated to be efficacious for the reduction of growth of small abdominal aortic aneurysms. N-TA³CT would be inconclusive with regard to treatment effect but may be informative as a Phase IIb clinical trial with regard to defining the defects in performance, e.g., insufficient treatment adherence, that must be addressed in designing a Phase III clinical trial. If the full analysis population analysis leads us to reject the null hypothesis and the per protocol population analysis leads to an effect size of similar magnitude to the full analysis population analysis but does not reject the null hypothesis, we will conclude that the per protocol analysis population analysis was insensitive and reject the null hypothesis. If the full analysis population analysis and the per protocol population analysis are contradictory – i.e., no similarity of effect size and no agreement on rejection of or failure to reject the null hypothesis – we will examine the results closely for an explanation of these pathological findings.

If we reject the null hypothesis with $\geq 40\%$ less growth in doxycycline group:

- An analysis without imputation will be performed. If the results of the analysis without imputation do not return an effect size similar to the primary outcome analysis, the rejection of the null hypothesis will be called into question as too highly dependent on imputation.
- Also, a per protocol analysis with an effect size similar to or larger than 40% would be supportive of the interpretation that a clinically significant effect was observed in the full analysis population, but if the per protocol analysis effect size were less than 40%, the clinical significance of the finding should be viewed as questionable.

If we reject the null hypothesis with a median growth less than 40% reduced in the doxycycline group as compared to the placebo group:

Non-Invasive Treatment of Abdominal Aortic Aneurysm Clinical Trial

N-TA³CT

STATISTICAL ANALYSIS PLAN

- Should the per protocol analysis be associated with an effect size greater than 40%, there could be reason for belief that a clinically significant benefit exists that would justify further investigation.
- Also, rejection of the null hypothesis with an effect size less than 40% but a large difference (e.g., doubling) of the proportion of patients whose aneurysms grew less than 1.0 mm or a large reduction (e.g., halving) of the proportion of patients whose aneurysms grew more than 6 mm would suggest the possibility of clinically significant benefit that would justify further investigation.

An alternative interpretation to be kept in mind whenever the null hypothesis is rejected is the occurrence of a difference by chance.

Failure to reject the null hypothesis:

Failure to reject the null hypothesis in the primary outcome analysis would be interpreted to mean that doxycycline did not have a beneficial effect size $\geq 40\%$ or that the design assumptions and performance were not of the quality necessary for a definitive test of the null hypothesis. If the effect size is $\geq 40\%$ but we do not reject the null hypothesis, we will examine the design assumptions and study performance carefully to report any deficiencies that may influence future investigations.

Non-Invasive Treatment of Abdominal Aortic Aneurysm Clinical Trial

N-TA³CT

STATISTICAL ANALYSIS PLAN

10 SAP Revision

Identify major changes. Only changes after sign-off need to be recorded.

Revision Date	Section	Summary of Revision	Reason for Revision

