3.3.5 Sample Size and Power

The study is designed to have greater than 90% power with a total sample size of 248 patients for a one-sided 0.025 test for an assumed reduction of 40% in the mean increase in aneurysm diameter from 2.5 mm/year to 1.5 mm/year. The calculations allow for a 10% non-adherence rate in the doxycycline treatment group and for 15% of participants to have a missing two-year CT scans. Additional details regarding the sample size and power calculations are contained in the protocol.

4 General Consideration for Data Analyses

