4.2.2 Multiple Comparisons

For the primary analysis, we consider a one-sided p-value of 0.0247 to be significant. It is less than 0.025 to account for the interim analyses. To account for the multiplicity of hypotheses being tested in secondary and exploratory analyses, a p-value < 0.01 will be required to consider there to be evidence of differences present, i.e. to reject the null hypothesis. We consider p<0.001 as strong evidence.

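### SAP section 9 judges the 40% target by the point estimate, at a value set before the non-adherence allowance, and gives no interval for deciding what non-rejection means

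*SAP*

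**What the plan says.** SAP section 3.3.5 claims "greater than 90% power with a total sample size of 248 patients" "for a one-sided 0.025 test", assuming a "reduction of 40% in the mean increase in aneurysm diameter from 2.5 mm/year to 1.5 mm/year". It then adds: "The calculations allow for a 10% non-adherence rate in the doxycycline treatment group", and allows "for 15% of participants to have a missing two-year CT scans". The SD is not given; details are left to the protocol. Section 4.2.2 sets the final threshold: "we consider a one-sided p-value of 0.0247 to be significant".

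Section 9 applies the 40% figure to the observed result in the full analysis population, which section 4.1.2 defines by assigned treatment and without regard to adherence.

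- **Null rejected, median growth at least 40% lower:** this "would be evidence of both a statistically significant and clinically significant effect". It is then checked against the analysis without imputation and the per-protocol effect size.
- **Null rejected, reduction below 40%:** a per-protocol effect above 40%, or large shifts in the proportions growing less than 1.0 mm or more than 6 mm, may justify further investigation.
- **Null not rejected:** this "would be interpreted to mean that doxycycline did not have a beneficial effect size" of 40% or more, or else that design assumptions and performance were not good enough for a definitive test. An observed effect of 40% or more without rejection gets its own instruction to examine design and performance.

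None of these branches uses a confidence interval.

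**The concern.** These rules turn the p-value into the trial's published conclusion, and two things about them are fixed badly.

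First, the cut for a clinically significant result equals the effect assumed before the non-adherence allowance, but it is applied where non-adherers are counted. A drug that works as designed would therefore be expected to fall somewhat short of the cut, and sampling error alone would decide which branch the trial lands in.

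Second, for a non-significant result the SAP offers two readings and no means of choosing. An interval would show whether the data exclude 40%. Without one, a trial whose data remain compatible with a 40% reduction could be reported as showing that no such effect exists. Ordinary type II error in a sound trial is not named as a possibility.

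**Working it through.** **Inputs.** From section 3.3.5: N = 248, power above 90%, one-sided 0.025, growth 2.5 versus 1.5 mm/year (5.0 versus 3.0 mm over 24 months), 10% non-adherence, 15% missing scans. From section 4.2.2: final one-sided level 0.0247 (z = 1.965). From section 3.3.4: equal allocation.

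**The plan's own figure.** The stated power cannot be reproduced because the SAP gives no SD. I back-solved the precision it implies, using a normal approximation to a comparison of two means.

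**Dilution.** Assume non-adherers grow as on placebo. The doxycycline mean is 0.9 × 3.0 + 0.1 × 5.0 = 3.2 mm. The difference is 1.8 mm, and 1.8/5.0 = 36%.

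**Implied precision.** SE of the difference = 1.8/(z for 0.025 + z for power).

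- 90% power: 1.8/(1.960 + 1.282) = 0.555 mm. With 248 × 0.85/2 = 105.4 per arm, SD = 0.555 × √(105.4/2), about 4.03 mm.
- 95% power: 1.8/(1.960 + 1.645) = 0.499 mm; SD about 3.6 mm.

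The SE does not depend on the number per arm used for the back-solve.

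**Chance of an observed reduction of at least 40%.** With D and P the observed arm values, the condition is D − 0.6P ≤ 0. Its expectation is 3.2 − 3.0 = 0.2 mm and its standard error is s√(1 + 0.36) = s√1.36, where s = SE/√2 is the standard error of one arm mean. So the probability is Φ(−0.2/(s√1.36)). For medians of normal data, s is multiplied by √(π/2).

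| Power | s (mm) | Means | Medians |
|---|---|---|---|
| 90% | 0.393 | 0.33 | 0.36 |
| 95% | 0.353 | 0.31 | 0.35 |

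Simulation of 10,000 trials per setting, requiring rejection at 0.0247 as well, gave 0.32-0.33 for means and 0.36-0.37 for medians. Rejection adds almost no restriction: at 90% power it needs an observed difference of only 1.965 × 0.555 = 1.091 mm, or 1.091/5.0 = 21.8%. With a true 40% reduction in the analysed population (no dilution), the probability is 0.50.

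**Non-rejection.** Let c = 1.965 × SE and G be placebo growth, with the interval for the difference expressed as a percentage of G. A result is non-significant if the observed reduction is below c/G. The interval still includes 40% if the reduction exceeds 0.40 − c/G. The last column is the probability of landing between the two limits when the true reduction is 36%.

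| Setting | Non-significant below | 40% inside interval above | Probability |
|---|---|---|---|
| 90% power as planned (SE 0.555, G 5.0) | 21.8% | 18.2% | 4.7% |
| 95% power as planned (SE 0.499, G 5.0) | 19.6% | 20.4% | none |
| SD 5 mm (SE 5 × √(2/105.4) = 0.689, G 5.0) | 27.1% | 12.9% | 21% |
| Placebo growth 4.0 mm (SE 0.555, G 4.0) | 27.3% | 12.7% | 22% |

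The SAP's separate instruction for a non-significant effect of 40% or more does not reach this window. With G = 5.0 mm it would need an SE above 2.0/1.965 = 1.02 mm, nearly twice the planned value.

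**The case against.** The strongest reply is that section 9 is more careful than a bare 40% cut suggests, and much of this stands.

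- A reader might infer that non-significance alone is taken to exclude 40%. The SAP does not say so. It offers the second reading, and section 9 also asks investigators who fail to reject to show that the test was sensitive, pointing to power assumptions, adherence and missing data. What survives is narrower: no quantity is named that would decide between the two readings.
- A reader might infer that a significant result below 40% is written off. It is not. The per-protocol and responder routes remain open, although they lead only to further investigation and not to the stronger conclusion.
- The 36% depends on how non-adherers grow, which the SAP does not state. Without dilution the figure is one in two, as for any true effect that equals a point threshold.
- The planned power is above 90%. At 95% the non-rejection window is empty, so non-significance would then exclude 40%. The 21-22% figures require departures from plan.
- The primary test is a normal-scores ANCOVA with worst ranks for events. A comparison of two means only approximates its significance boundary.
- An interval would not raise the one-in-three. Nor may 40% lying inside the interval stand in for clinical significance: at 90% power a result just at significance (21.8%) has an upper limit of 43.6%, so essentially every significant result would qualify.

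**Conclusion.** The point holds in a limited form. Section 9 reads the 40% target from a point estimate, in a population where the design's own allowance puts the expected reduction at about 36%, and it gives no interval for interpreting non-rejection. A trial performing as designed would meet the joint criterion about 31-37% of the time, or about 50% with no dilution. The non-rejection problem is small at planned precision (4.7% of trials with a true 36% effect at exactly 90% power, none at 95%). It becomes material, at 21-22%, if the SD is 5 mm or placebo growth is 4.0 mm.

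These figures assume a back-solved SD, normally distributed growth, equal percentage reductions in mean and median, and placebo-rate growth in non-adherers. The SAP does not say how median growth is computed for deaths, ruptures and repairs, so their effect is not modelled. The primary test, its significance level and the sample size are not in question; only the rules for interpreting the result are.

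**What to change.** In section 9:

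- Report the percentage reduction in median growth with a confidence interval matched to the one-sided 0.0247 test, that is a two-sided level of 1 − 2 × 0.0247 = 95.06%, obtained by bootstrap or from the multiply imputed data.
- State that a 40% effect is ruled out only if the upper limit is below 40%. Otherwise call a non-significant result inconclusive for 40%.
- For a significant result, give the estimate and interval next to the 40% target. Do not call the result clinically significant merely because 40% lies inside the interval.
- Say whether 40% means the effect under full adherence or the effect in the full analysis population. If the point cut is kept, state that the design's expected value in the full analysis population is about 36% when non-adherers grow at the placebo rate.

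The cost is some wording and one additional interval. The downside is that some results will be labelled inconclusive on the 40% target.

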4.1.2 Full Analysis Population

The full analysis population includes all patients randomized except those with no follow-up contact and no follow-up CT scan, analyzed by treatment assigned at randomization. Because

Non-Invasive Treatment of Abdominal Aortic Aneurysm Clinical Trial

N-TA³CT

STATISTICAL ANALYSIS PLAN

treatment was never started and because the primary endpoint is not known and cannot be reasonably imputed in participants with no follow-up and no follow-up CT scan, analysis of the primary endpoint will be conducted on the *full analysis population*.

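### Section 9 makes a significant primary result depend on an undefined 'similar' per-protocol effect when the per-protocol test does not reject, and leaves one case without a decision

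*SAP*

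**What the plan says.** **The primary test.** SAP 4.1.2 assigns the primary endpoint analysis to the full analysis population. SAP 4.2.2 sets its level: "For the primary analysis, we consider a one-sided p-value of 0.0247 to be significant". For secondary and exploratory analyses the same section says "a p-value < 0.01 will be required to consider there to be evidence of differences present", without giving the side.

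**The per-protocol analysis.** SAP 8.3 reads in full: "An analysis will be performed using the methodology described above for the primary endpoint, based on the per-protocol population". It names no significance level. By SAP 4.1.3 the population is selected on an available two-year scan or a clinical event, and on reported intake of at least 80% of expected doses.

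**The decision rule.** Section 9, in the part on conflict between the two populations, covers four situations:

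- Both analyses agree: "in agreement rejecting the null hypothesis or failing to reject the null hypothesis, we will reject or fail to reject the null hypothesis accordingly".
- The full analysis fails and per-protocol rejects: efficacy is not demonstrated and the trial is inconclusive on treatment effect.
- The full analysis rejects, per-protocol does not, and the effect sizes are similar: per-protocol is judged insensitive and the null is rejected.
- The analyses disagree and the effect sizes are not similar: "we will examine the results closely for an explanation of these pathological findings".

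**The concern.** A primary test fixed in advance should settle the primary hypothesis by itself. Here a significant result in the full analysis population can meet a further condition, set by a subset chosen on what happened after randomisation (adherence and scan availability). The condition turns on the word similar, for which the SAP gives no margin and no scale. The scale matters: the model in 8.1 estimates a difference in normal scores, while Section 9 elsewhere describes effects as a percentage reduction in median growth. Two analysts could place the same data in the rejecting situation or in the undecided one.

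In the last situation the plan commits to no conclusion, so a trial that met its primary criterion could be reported either way, with the choice made after unblinding. The stated power belongs to the full analysis test alone, not to this two-part rule.

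**Working it through.** **1. Every combination under Section 9**

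| Full analysis | Per-protocol | Effect sizes | Outcome stated |
|---|---|---|---|
| rejects | rejects | any | reject |
| rejects | does not | similar | reject |
| rejects | does not | not similar | none; results examined |
| fails | fails | any | fail to reject |
| fails | rejects | similar | not demonstrated, inconclusive |
| fails | rejects | not similar | two statements apply: inconclusive, and results examined |

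Row 3 is the gap. Row 6 is an overlap with less at stake, since neither statement claims efficacy. Both rejecting rows need a significant full analysis, so the rule cannot reject more often under the null than the primary test does.

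**2. The plan's power figure**

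SAP 3.3.5 gives 248 patients, more than 90% power, one-sided 0.025, growth of 2.5 against 1.5 mm/year, 10% non-adherence and 15% missing scans. It gives no SD, so the power cannot be recomputed directly. Solving for the SD:

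- Two-year difference: 2 × (2.5 − 1.5) = 2.0 mm; diluted by 10%, 1.8 mm.
- Patients per arm: 248 × 0.85 / 2 = 105.4.
- SD = 1.8 / [(1.960 + 1.282) × √(2/105.4)] = 4.03 mm.

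The stated power holds if the SD is at most about 4.03 mm with both allowances (4.86 mm with neither). It is neither confirmed nor refuted. The next step takes 90% power as given and needs no SD.

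**3. How often row 3 occurs**

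Let f be the per-protocol share of the full analysis set. Scale the full-set estimate to variance 1. Then

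- full estimate = f × (per-protocol estimate) + (1 − f) × (estimate in the rest);
- variances are 1/f for per-protocol and 1/(1 − f) for the rest;
- true mean = z(0.0247) + z(0.90) = 1.965 + 1.282 = 3.247, the same in both sets;
- full analysis rejects if its estimate exceeds 1.965; per-protocol rejects if √f × its estimate exceeds the critical value for its level;
- row 3 occurs if full rejects, per-protocol does not, and the per-protocol estimate is below s × the full estimate.

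The values of f and s, and the per-protocol level, are assumptions. Results from 1,000,000 draws per setting, as a share of significant full analyses, with per-protocol tested at one-sided 0.0247:

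| f | per-protocol does not reject | row 3, s = 80% | row 3, s = 50% |
|---|---|---|---|
| 0.7 | 15.5% | 9.7% | 1.2% |
| 0.8 | 9.7% | 5.4% | 0.3% |
| 0.9 | 4.9% | 1.8% | 0.01% |

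The second column is not the harm, because Section 9 still rejects when the effects are similar. Columns three and four are.

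**4. Sensitivity**

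- Per-protocol tested at one-sided 0.01 instead: row 3 at s = 80% becomes 12.7%, 7.4% and 2.5%.
- True per-protocol effect larger by 1/0.9 (level 0.0247, s = 80%): 3.8%, 1.4% and 0.1%.

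**5. Cost in power if row 3 is counted as not rejecting**

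At s = 80%: 0.900 × (1 − 0.097) = 0.813 for f = 0.7, 0.900 × (1 − 0.054) = 0.851 for f = 0.8, and 0.900 × (1 − 0.018) = 0.884 for f = 0.9. At s = 50% and f = 0.7: 0.900 × (1 − 0.012) = 0.889.

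**The case against.** The best defence is that Section 9 is interpretation. It describes a Phase IIb trial that will not lead to a labelled indication, and it says that the primary analysis in the full analysis population may reject or fail to reject. The agreement clause can never alter the full analysis decision. Most combinations have a stated outcome, and the open one needs both disagreement and dissimilar effects. Discussing a discordant per-protocol result is good practice.

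Much of this stands, and it limits the size of the point. It does not close the gap: the section is written as a rule on when the null will be rejected, and for row 3 the rule stops short.

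Four stronger readings are tempting, and the SAP does not support them:

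- *Rejection requires per-protocol agreement.* It does not. A non-significant per-protocol result with a similar effect still leads to rejection.
- *The per-protocol test carries a stricter threshold of 0.01.* That level is set for secondary and exploratory analyses, and nothing labels the per-protocol analysis as either. SAP 8.3 points to the primary methodology, and Section 9 speaks of primary outcome analyses in both populations. Where Section 9 wants the secondary standard, as for non-significant gender differences, it says so. The fault is that the level is unstated.
- *Section 9 contradicts itself on a failed primary test.* It says "Failure to reject the null hypothesis in the primary outcome analysis would be interpreted to mean that doxycycline did not have a beneficial effect size" of 40% or more, but adds the alternative that design assumptions or performance fell short. The inconclusive label for a failed full analysis with a per-protocol rejection fits that alternative.
- *The per-protocol analysis can rescue a failed trial or inflate type I error.* Section 9 says efficacy is then not demonstrated, and no route to rejection bypasses a significant full analysis.

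**Conclusion.** The point holds in a limited form. Section 9 does not let the pre-specified primary test decide the null hypothesis alone. When the full analysis rejects and per-protocol does not, the outcome rests on an undefined term, and one of the two possibilities has no stated decision. The per-protocol level is unspecified, and one combination falls under two statements.

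The harm is a loss of power that is modest in most settings, and discretion after the data are seen. With 90% power, equal true effects, a per-protocol set of 70-90% and a per-protocol level of one-sided 0.0247, about 2-10% of significant full analyses end undecided if similar means at least 80% of the full effect. The figure is about 1% or less if it means at least 50%. The per-protocol share, its level, the equal effects and both margins are assumptions, not SAP figures. That the answer moves this much with the meaning of one word is the main reason to settle it before the analysis.

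**What to change.** Replace the paragraph in Section 9 on conflict between the two populations with wording such as:

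*The test in the full analysis population at one-sided 0.0247 alone decides whether the null hypothesis is rejected. The per-protocol analysis is supportive; its estimate and confidence interval will be reported. Any discordance will be discussed but will not change or suspend that decision.*

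This takes the undecided share to zero, removes the overlap, and leaves the error rate and power as those of the primary test. The per-protocol analysis may still be described as rejecting or not rejecting; that no longer affects the decision.

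The cost is a change of SAP wording, with no new data or analyses. The small downside is that the sponsor gives up the option of leaving the conclusion open when the two analyses differ.
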